7.5. Concomitant Medications

7.5.1. Permitted Concomitant Medications

For all study parts, a stable dose and regimen of any medication(s) (prescription or OTC) that the subject is taking regularly (i.e., medications for chronic conditions such as hypertension, high cholesterol, or depression must be unchanged in dose or type for at least 6 months for Part A or 3 months for Parts B, C, and D) is permitted, except those listed in Section 7.5.2. Additionally, use of the following is also permitted:

- Oral, injectable, subdermal, intravaginal, or implantable contraceptives, as well as intrauterine device, and intrauterine hormone-releasing system are permitted for contraception
- Paracetamol (< 2g/day), aspirin (\leq 3g/day), or ibuprofen (< 1.2 g/day)
- Antihistamines

Investigators may initiate new prescription and non-prescription concomitant medications or treatments deemed necessary to provide adequate care for AEs or other new onset medical conditions, except those listed in Section 7.5.2.

7.5.2. Prohibited Concomitant Medications

Use of any of the following systemic medications within 14 days before study drug administration and throughout the study (unless otherwise noted) is prohibited:

- Paracetamol (acetaminophen) \geq 2 g/day, aspirin > 3 g/day or ibuprofen \geq 1.2 g/day

- Tricyclic antidepressants
- Valproate
- Phenytoin
- Amiodarone
- Anabolic steroids
- Allopurinol
- Amoxicillin-clavulanate
- Minocycline
- Nitrofurantoin
- Sulfamethoxazole/trimethoprim
- Erythromycin
- Isoniazid
- Rifampin
- Azole antifungals
- Steroids (prednisone equivalent of > 5 mg/day) or other immunosuppressive agent (Note: corticosteroid administration for the treatment of immune-mediated AEs is allowed.)
- Herbal remedies within 28 days before study drug administration and throughout the duration of the study
- Part D only: antiviral therapy for chronic HBV infection within 6 months prior to screening and through the Week 8 visit
 - If, in the opinion of the investigator, antiviral therapy for chronic HBV infection is urgently indicated at any time between screening and the Week 8 visit, antiviral therapy for chronic HBV infection may be initiated at any time
 - For patients in extended follow-up, NRTI or interferon therapy may be initiated after the Week 8 visit if clinically indicated and after discussion with the Sponsor Medical Monitor (or designee)

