 26. Received an investigational agent within 90 days or 5 half-lives (if known), whichever is longer, before study drug administration or are active in the follow-up phase of another clinical study involving interventional treatment. Subjects must also agree not to take part in any other study at any time during their participation in this study, inclusive of the follow-up period.
 27. Prior receipt of an oligonucleotide drug (eg, siRNA, antisense oligonucleotide) with activity against HBV

28. Any illness or medical condition other than chronic HBV infection that makes the subject unsuitable for participation in the study
29. Part D only: Receipt of NRTI therapy, interferon, or any other antiviral therapy with activity against HBV within 6 months prior to screening
30. Part D only: In the opinion of the investigator, anticipated to require to antiviral therapy for chronic HBV infection at any time during the screening period or within 8 weeks after study drug administration

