- ^q Study drug will be administered via SC injection as described in Section 7.3.5 .
- ^r On Day 1, blood samples for PK analysis will be collected predose and at 1 hour, 4 hours, and 6 hours post-dose. Includes samples for free and total PK assays, as applicable.
- ^s Includes samples for ADA and neutralizing antibodies (NAb), as applicable. Additional unscheduled samples for immunogenicity analysis may be collected if an immunologic related event is suspected. Immunogenicity sampling beyond the planned follow-up period may occur based on emerging results. Further details can be found in Section 8.16 .
- ^t Should only be collected for Part C and D subjects who are HBeAg qualitative positive at screening.
- ^u If a subject experiences ALT flare (as defined by >2-fold increase in ALT relative to Day 1 predose ALT), additional HBV DNA quantitation and HBV resistance surveillance sample(s) may be collected
- ^v HBV DNA samples at the Day 2 Day 4 Week 8 and Week 40 will be collected as directed

CCI

CCI

^y See Sectio

CCI

^{aa} O Da

itte as

needed for follow up of any unresolved local tolerability symptoms.

^{bb} All AEs related to screening activities must be collected starting at the time of consent; any other events occurring during the screening period should be reported as medical history. All SAEs must be collected from the time of consent onwards. All AEs will be collected through the Week 8/ET visit. Following Week 8, only targeted AEs and SAEs need to be collected through the end of the study. Further details can be found in Section 9.3 .

^{cc} For Parts B and C only; NRTIs will be continued through the end of follow-up for each subject. Subjects in Part D will not receive NRTI therapy.

**APPENDIX 4. PART A PHARMACOKINETIC TIMEPOINTS
 (SC INJECTION)**

Study Day \pm window in days (Study Week)	Protocol Time	Blood PK (serum)
Day 1	Predose	X
	Dose	
	1 hour	X
	4 hours	X
	6 hours	X
Day 2	24 hours	X
Day 4 \pm 1		X
Day 8 \pm 1 (Week 1)		X
Day 15 \pm 2 (Week 2)		X
Day 29 \pm 2 (Week 4)		X
Day 57 \pm 7 (Week 8)		X
Day 85 \pm 7 (Week 12)		X
Day 127 \pm 7 (Week 18)		X
Day 169 \pm 7 (Week 24)		X

**APPENDIX 5. PART A PHARMACOKINETIC TIMEPOINTS
 (IV INFUSION)**

[figure not shown]
Study Day \pm window in days (Study Week)	Protocol Time	Blood PK (serum)
Day 1	Predose	X
	Dose	
	End of infusion	X
	1 hour post-end of infusion	X
	4 hours post-end of infusion	X
	6 hours post-end of infusion	X
Day 2	24 hours post-end of infusion	X
Day 4 \pm 1		X

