6. STATISTICAL ANALYSES

6.1. General Considerations

The study assessments and time points schedule are provided in the study protocol. All individual participant data for those who were randomized to study intervention will be presented in data listings.

Continuous variables will be summarized using the following descriptive summary statistics: the number of participants (n), mean, standard deviation (SD), median, minimum value (min), and maximum value (max), unless otherwise specified.

In general, the precision of the measurement for each continuous variable will be used to determine the number of decimal places to present in tables, figures, and derived listings. Unless otherwise specified, raw data will be presented with the same number of decimals as collected, and derived data will be presented with an appropriate number of decimals based on general practice, mathematical rationale, or scientific rationale. Any values that require transformation to standard units (metric or SI) will be converted with the appropriate corresponding precision.

Categorical variables will be summarized using counts and percentages. Generally, percentages will be presented to 1 decimal place.

Baseline Value: Unless otherwise specified, the baseline value will be defined as the most recent non-missing (scheduled or unscheduled) measurement collected prior to the administration of study intervention.

If multiple measurements that are prior to dosing are recorded on the same date and with the same time or if time is not available, then the average of these measurements will be considered the baseline value.

Absolute change from baseline will be calculated as post-baseline value - baseline value.

Treatment-emergent (TE) period: Unless otherwise specified, the TE period will include the time from the administration of study drug until the Week 24 visit (or the Day 169, if the Week 24 visit is unavailable) for Part A, and the Week 8 visit (or the Day 57, if the Week 8 visit is unavailable) for Part B, C, and D.

Unscheduled visits: Unscheduled visit measurements will be included in analysis as follows:

1. In scheduled visit windows per specified visit windowing rules, if applicable
2. In the derivation of baseline and last follow-up measurements
3. In the derivation of maximum and minimum values and/or maximum and minimum change from baseline values during follow-up period or TE period
4. In individual participant data listings as appropriate

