6.7.2. Analysis Methods

HBV viral parameters (quantitative), the raw values and the absolute change from baseline at each post-baseline visit up to Week 8 visit will be summarized descriptively (n, mean, SD, median, Q1, Q3, min, max) by VIR-3434 treatment cohort and placebo.

Similarly, the raw values and the change from baseline at nadir during the follow-up period up to Week 8 in HBsAg and HBV DNA (Part D only) will be summarized descriptively (n, mean, SD, median, Q1, Q3, min, max) by VIR-3434 treatment cohort and placebo.

In addition, mean (\pm SD) of change from baseline in HBsAg (Part B, C, and D) and HBV DNA (Part D only) will be plotted at each post-baseline visit up to Week 8 by VIR-3434 treatment cohort and placebo.

HBeAg loss, HBsAg loss, Anti-HBs seroconversion, and Anti-HBe seroconversion: the percentage and number of participants who ever met each of the variables during the follow-up period up to Week 8 will be summarized and presented by VIR-3434 treatment cohort and placebo.

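### In Part D, HBV DNA values taken after urgently started antiviral therapy still enter the Week 8 nadir and by-visit changes, so that therapy's effect can be credited to VIR-3434 or placebo

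*Protocol*

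**What the plan says.** **The default and its exception.** Protocol 7.5.2 lists as prohibited "Part D only: antiviral therapy for chronic HBV infection within 6 months prior to screening and through the Week 8 visit". A sub-bullet lifts this where, in the investigator's opinion, such therapy "is urgently indicated at any time between screening and the Week 8 visit". In that case "antiviral therapy for chronic HBV infection may be initiated at any time".

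**Safeguard at entry.** Exclusion 30 (Protocol 6.5) removes Part D candidates whom the investigator expects to need antiviral therapy "at any time during the screening period or within 8 weeks after study drug administration". It cannot remove a need that nobody foresaw.

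**A conflicting statement.** Footnote cc of the Parts B, C and D schedule of assessments (Protocol Appendix 3) says "Subjects in Part D will not receive NRTI therapy", without mentioning the exception.

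**The endpoint and its derivation.** Protocol 4.2 makes maximum change in HBV DNA from Day 1 predose a secondary endpoint for Part D only. SAP 6.7.2 summarises "the change from baseline at nadir during the follow-up period up to Week 8 in HBsAg and HBV DNA", by cohort and placebo, on the Full Analysis Set (SAP 6.7). It also summarises and plots change at each visit to Week 8. Under SAP 6.1, unscheduled measurements are used "In the derivation of maximum and minimum values and/or maximum and minimum change from baseline values during follow-up period or TE period". For by-visit summaries, SAP Appendix 2 takes the scheduled value in a window and falls back on an unscheduled one.

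**Extra sampling.** Footnote u of Protocol Appendix 3 provides that after an ALT flare "additional HBV DNA quantitation and HBV resistance surveillance sample(s) may be collected".

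**The concern.** Part D enrols subjects who are not on NRTI therapy, and it is the only Part in which HBV DNA change is an endpoint. The change is meant to describe what a single dose of VIR-3434 does. The protocol foresees that another anti-HBV drug may start inside the measurement window, but the SAP does not say what then happens to the data.

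A nadir is exposed to this because it keeps the lowest value, whatever caused it. If a value after antiviral start is lower than any before it, that value becomes the subject's result. In an active cohort this overstates VIR-3434 activity. In placebo it hides activity by narrowing the contrast. By-visit means and plots carry the same values, and the exposure-response work in Protocol 10.5 could inherit them. With six active subjects per cohort, one case is visible in the mean.

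**Working it through.** **1. Is there a rule elsewhere?** I checked the SAP sections where one could sit.

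| Place | Content on values after antiviral start |
|---|---|
| SAP 5.2 (Full Analysis Set) | Randomised and dosed; no exclusion |
| SAP 6.1 (missing data, unscheduled visits) | Detection-limit and inclusion rules only |
| SAP 6.2.4 | Concomitant medication summarised by preferred name |
| SAP 6.7.1, 6.7.2 | Window to Week 8; no cut-off |
| SAP 6.8.1 | No such modification listed |
| SAP Appendix 2 | Visit windows only |

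No estimand or treatment-policy choice is stated. SAP 6.7 shows no redaction.

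**2. Group sizes.** Each cohort has a sentinel pair randomised 1:1 and six further subjects randomised 5:1, giving 6 active and 2 placebo. Three Part D cohorts give 3 × 8 = 24, as stated in Protocol 6.1. SAP Table 2 shows 1d and 2d enrolled and 3d not. The planned numbers are therefore 6 active per cohort and, with placebo pooled within Part by route (Protocol synopsis), 2 × 2 = 4 placebo; 16 in all.

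**3. Shift in a mean.** If one subject has x log10 of fall beyond the nadir otherwise reached, the mean of n subjects moves by x/n. The documents give no HBV DNA effect for antiviral therapy over eight weeks, so x = 1 to 3 is an assumption.

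| x (assumed) | Active cohort, n = 6 | Pooled placebo, n = 4 |
|---|---|---|
| 1 | 1/6 = 0.17 | 1/4 = 0.25 |
| 2 | 2/6 = 0.33 | 2/4 = 0.50 |
| 3 | 3/6 = 0.50 | 3/4 = 0.75 |

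**4. What limits x.** Only the part of the fall below the earlier nadir counts. As an illustration, if an active subject has already fallen 2.0 log10 and later reads 2.5 log10 below baseline on therapy, x = 0.5 and the cohort mean moves by 0.5/6 = 0.08. If the later value is no lower than the earlier nadir, x = 0. A late start leaves little time before Week 8. There is also a floor: entry requires HBV DNA of at least 1,000 IU/mL (3 log10) at screening, and SAP 6.1 sets a not-detected result to 0 on the log scale when the detection limit exceeds 1. A subject with a baseline of 3 log10 then cannot fall more than 3 log10 from all causes together.

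**5. How often.** The documents give no rate. For an assumed rate p, the chance of at least one case among 16 is 1 − (1 − p)^16: 28% at p = 2%, 56% at 5% and 82% at 10%.

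**6. HBsAg.** Protocol 2.3.2 cites a mean HBsAg decline of 0.3 log10 over 48 weeks of NRTI. Pro-rated to eight weeks this is 0.3 × 8/48 = 0.05 log10. One subject then moves a mean by 0.05/6 = 0.008 (active) or 0.05/4 = 0.013 (placebo). Even if the full 0.3 came by Week 8, the shifts would be 0.05 and 0.075. The documents give no eight-week HBsAg figure for interferon.

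**The case against.** The strongest reply is that this is a narrow exception in a small descriptive study. Therapy is prohibited by default, exclusion 30 screens out the expected cases, and footnote cc suggests none are planned. There are no hypotheses (SAP 4), so no error rate is at stake. SAP 6.7.2 also reports median, quartiles and range, and the individual listings would let a careful reader find an affected subject. Using all observed data is a recognised choice.

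Much of this stands. The event may never occur, and no inference fails if it does. Several stronger readings do not stand:

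- A reader might infer that Part D freely allows antiviral therapy before Week 8. It does not; the allowance depends on urgent need.
- A reader might infer that any single sample after antiviral start fixes the subject's result. It does so only if it is lower than the value already reached.
- A reader might treat HBsAg as equally exposed. The protocol's own NRTI figure makes that effect negligible.
- A reader might assume a larger extra fall, such as 4 log10, which would give 4/6 = 0.67 and 4/4 = 1.0. Nothing in the documents supports that, and the floor in step 4 rules it out for a subject with a baseline of 3 log10.
- A reader might see the ALT-flare samples as the source of the problem. Footnote u permits them but does not mention antiviral therapy. The scheduled Week 8 sample alone is enough.

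The reply does not supply a rule. The all-data choice is not stated as a choice. Because the sponsor is not blinded (SAP 3.4), deciding case by case after seeing the values is the option to avoid.

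**Conclusion.** The gap is real and confined to Part D HBV DNA. The protocol foresees antiviral start before Week 8 in urgent cases, and the SAP derivation then attributes any lower value to the assigned study drug. Under the assumed 1 to 3 log10 of extra fall, one case shifts a 6-subject cohort mean by 0.17 to 0.50 log10 and the planned 4-subject pooled placebo mean by 0.25 to 0.75 log10. These are conditional figures: they need a case to occur, enough time on therapy before Week 8 and, for the nadir, a value below the one already reached. The documents do not support saying that the reported result will be wrong, only that the plan leaves it unprotected. For HBsAg the principle is the same, but the NRTI effect is negligible.

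**What to change.** In SAP 6.7.2, for Part D:

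- Derive the HBV DNA nadir and by-visit changes from values up to the first dose of any non-study anti-HBV therapy. The same rule may be applied to HBsAg for consistency.
- Report the number of affected subjects by arm and flag them in the listings.
- Show the all-data result as a sensitivity line.

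The cost is one SAP rule and one extra summary line, with start dates taken from the concomitant medication data the SAP already uses. There are two downsides. Affected subjects have a shorter window in which to reach a nadir, and because they are selected by clinical need the truncation is informative; the all-data line and the counts by arm let a reader judge it. The cut-off also depends on the start date. SAP Appendix 3 imputes a missing day to the first of the month, and a wholly missing date to a date before dosing, either of which could discard valid values. The actual start date should be queried rather than imputed for this purpose.

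Separately, Protocol 7.5.2 and footnote cc of Protocol Appendix 3 contradict each other on whether a Part D subject can receive an NRTI, and must be reconciled. This point takes no view on when antiviral therapy should be given.

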7.5.3. NRTI Therapy (Parts B and C)

Examples of permitted NRTI therapy include, but are not limited to, the following:

- Tenofovir disoproxil/tenofovir alafenamide
- Entecavir
- Lamivudine
- Adefovir/adefovur dipivoxil

8. STUDY PROCEDURES

The Schedule of Study Assessments is provided in [Appendix 2](#) for Part A and [Appendix 3](#) for Parts B, C, and D. Unscheduled visits are permitted at the discretion of the investigator as needed for safety assessment. Fasting is not required for any study procedure/assessment

8.1. Written Informed Consent

The subject's signed and dated informed consent must be obtained before conducting any study procedures.

8.2. Medical History

A complete medical history, including details regarding illnesses and allergies, date(s) of onset, and whether condition(s) is currently ongoing, prior HBV treatment history (Parts B, C, and D only), and HBV genotype (if available; Parts B, C, and D only), will be collected on all subjects during screening and should be updated prior to dosing.

8.3. Full Physical Examination

A full physical examination will include general appearance, head, neck, chest/respiratory, heart/cardiovascular, gastrointestinal/liver, extremities, skin, and screening neurological assessments.

8.4. Symptom-directed Physical Examination

A symptom-directed physical examination will be performed according to investigator discretion.

8.5. Weight and Height

Body weight and height will be measured.

8.6. Vital Signs

Vital sign measurements include blood pressure, pulse rate, temperature (oral preferred), and respiratory rate. Vital signs should be measured after the subject has rested comfortably for approximately 10 minutes. When scheduled at the same timepoints, the assessments of vital signs and 12-lead ECGs must be performed before the blood sample collections.

8.7. Electrocardiogram

12-lead safety ECGs will be recorded and reviewed on-site by the investigator at the timepoints outlined in [Appendix 2](#) and [Appendix 3](#). All ECGs should be measured in the supine position after the subject has rested comfortably for approximately 10 minutes.

8.8. Pregnancy Testing

A pregnancy test or confirmation of post-menopausal status must be confirmed for all female subjects. Post-menopausal status is defined as no menses for 12 months without an alternative medical cause. Pregnancy tests will be performed for WOCBP only. Pregnancy testing will be

performed per the SoA and any time pregnancy is suspected. A WOCBP who is known to be pregnant or who does not have a negative pregnancy test at screening is not eligible for study participation. A blood pregnancy test will be performed at screening and urine pregnancy tests will be performed thereafter. During the study, the results of these pregnancy tests must be known prior to study drug administration. A WOCBP determined to be pregnant while on study will be followed until the pregnancy outcome is known, as described in Section 9.4.2.

8.9. FibroScan

To exclude the presence of cirrhosis, subjects in Parts B, C, and D will have a FibroScan evaluation. This is not required to be performed if the subject has had a FibroScan in the 6 months prior to screening or liver biopsy in the year prior to screening that confirmed the absence of Metavir F3 fibrosis or F4 cirrhosis.

8.10. Screening Viral Serology Parameters

Screening viral serology parameters are as follows:

- **Part A:** Active infection with HIV, HCV, and HBV
- **Parts B, C, and D:** Active infection with HIV, HCV, and hepatitis Delta virus. Subjects who have positive HCV serology result must have HCV-RT PCR reflex testing to determine eligibility.

8.11. Screening Confirmation of Chronic HBV Infection

For Parts B, C, and D, chronic HBV infection will be determined at screening and is defined as the following:

- Positive serum HBsAg, HBV DNA, or HBeAg on 2 occasions at least 6 months apart based on previous or current laboratory documentation (any combination of these tests performed 6 months apart is acceptable)

8.12. Local Tolerability

For all study parts, a local tolerability assessment will be performed per the Schedule of Assessments for subjects receiving study drug by SC injection. Injection site(s) will be marked and mapped for later observation and should be documented. Injection site(s) should be monitored for pain/tenderness, swelling, redness, bruising, and pruritus.

The timing of local tolerability assessments for Part A can be found in [Appendix 2](#). The timing of the local tolerability assessments for Parts B, C, and D can be found in [Appendix 3](#).

At the discretion of the investigator, unscheduled visits are permitted as needed for follow up of any unresolved local tolerability symptoms.

8.13. Clinical Laboratory Assessments

Clinical laboratory tests that will be performed in this study are presented in [Appendix 9](#). In the event of an unexplained clinically relevant abnormal laboratory test occurring after study drug administration, the test may be repeated and followed up at the discretion of the investigator until

it has returned to the normal range or stabilized, and/or a diagnosis is made to adequately explain the abnormality.

8.14. Screening for Drugs of Abuse

For all parts of the study, urine will be collected for drugs of abuse screening. Panel will include amphetamines, cocaine, methadone, and opiates.

